Treatment and Follow-Up Period: During the 14-week treatment period, participants will visit the site Q2W on days 1, 15, 29, 43, 57, 71, and 85 (± 3 days) for investigational medicinal product (IMP) administration (7 visits), as well as an end-of-treatment visit on day 99 (± 3 days; week 14). After the end of the 14-week treatment period, all participants may be offered the option to enter a long-term extension trial described in a separate protocol (TV48574-IMM-20038). If they enter the long-term extension trial, they will not need to complete the follow-up visit in this trial. All other participants will return to the site for a follow-up visit (day 127 [± 3 days]). For those participants who enter the long-term extension trial, adverse events and concomitant medication data will be recorded in the dose-ranging trial case report form (CRF) up until the date of extension trial randomization (defined as the trial completion date for the dose-ranging trial). For those participants who screen fail the long-term extension trial, adverse events and concomitant medication data will be recorded in the dose-ranging trial up until the follow-up visit (day 127 [± 3 days]) CRF. Participants who complete the last scheduled visit will be considered to have completed the trial.

Participants who withdraw from the trial before completing the 14-week- treatment period will complete the assessments for the early termination visit and will be encouraged to complete the follow-up period in the trial.

The end of the trial is defined as the last visit of the last participant.

The total duration of participation in the trial is planned to be up to 24 weeks for each individual participant.

Trial procedures and assessments with respective time points are shown in Table 4 of the Trial Protocol.

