8. SAFETY ANALYSIS

8.1. General

The safety analysis set will be used for all safety analyses. Summaries will be presented by treatment and pooled TEV-45874, separately by indication (UC or CD) and pooled (UC and CD). The summaries will include participants in the 1800 mg treatment group that were randomized prior to PA03Rev01.

If an indication is stopped for safety reasons (see Section 13.1), pooled analyses of UC and CD will not be presented.

Safety listings will include all data collected, starting from screening. Safety summary tables will include all treatment-emergent data, ie, data collected from first day of trial drug until the end of the trial (including the FU period), unless specified otherwise.

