8.3. Adverse Events

All adverse events (AEs) will be coded using MedDRA. Common Terminology Criteria for Adverse Events (CTCAE) will be used to grade the severity of AEs. Treatment-emergent adverse events (TEAEs) are defined as AEs that start either on or after the first dose of the study drug and until first dose in study TV48574-IMM-20038 (if enrolled) or end of the FU period of the current study.

An overview table summarizing the following AE categories will be presented:

- Participants with at least 1 TEAE
- Participants with at least 1 TEAE CTCAE grade 3/4
- Participants with at least 1 treatment-related TEAE (related to IMP)
- Participants with at least 1 device-related TEAE
- Participants with at least 1 treatment-related TEAE CTCAE grade 3/4
- Participants with at least 1 serious TEAE
- Participants with at least 1 serious IMP related TEAE

- Participants with at least 1 serious device related TEAE
- Participants with at least 1 TEAE leading to discontinuation from the trial
- Participants with at least 1 TEAE leading to dose interruption
- Participants with at least 1 TEAE leading to treatment discontinuation
- Participants who died
- Participants with at least 1 protocol-defined TEAE of special interest (AESI)

Summaries will be presented for all TEAEs, and for the TEAE categories listed above.

The incidence of TEAEs will be summarized (overall and by grade) using descriptive statistics by SOC and PT (all TEAEs overall will also be presented by PT category in descending order of incidence in the pooled TEV-48574 group). Participants are counted only once in each SOC category, and only once in each PT category. For the summaries by grade, participants are counted at the highest grade. TEAEs that are missing information on seriousness will be excluded from the summary of serious TEAEs but included in the summary of non-serious TEAEs.

A Beta-binomial analysis of the 4 types of AEs used to define the stopping criteria in the interim safety analyses (see Section 13.1 and [Appendix 1](#)) will be conducted using the final data. The posterior probability that the AE rate in each active group and the 3 dose levels combined is larger than the AE rate in the placebo group will be reported for UC and CD separately and across the entire trial population.

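### TEAEs are counted to the first extension dose for participants who roll over but to day 127 for other completers, and the crude AE comparisons make no allowance for the difference

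*SAP*

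**What the plan says.** **TEAE window.** SAP Section 8.3 counts events starting on or after the first dose "until first dose in study TV48574-IMM-20038 (if enrolled) or end of the FU period of the current study". Section 8.1 fills the safety summary tables with "data collected from first day of trial drug until the end of the trial (including the FU period), unless specified otherwise".

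**Timeline.** Section 2.1 schedules "an end-of-treatment visit on day 99 (± 3 days; week 14"), after which "all participants may be offered the option to enter a long-term extension trial described in a separate protocol". For those who accept: "If they enter the long-term extension trial, they will not need to complete the follow-up visit in this trial". For the rest: "All other participants will return to the site for a follow-up visit (day 127 [± 3 days"]). Extension screen failures also stay under observation: "adverse events and concomitant medication data will be recorded in the dose-ranging trial up until the follow-up visit". Participants who withdraw during treatment have an early termination visit and are only encouraged to complete follow-up.

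**End of recording for extension entrants.** Section 2.1 has AEs recorded in this trial's CRF "up until the date of extension trial randomization (defined as the trial completion date for the dose-ranging trial"). That is extension randomisation, whereas Section 8.3 uses the first extension dose.

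**Analysis.** Section 8.3 summarises TEAEs as participant counts and percentages. It also reports, for the four AE types behind the stopping rules, the posterior probability that the active rate exceeds the placebo rate. In Appendix 1 that model takes only the number of participants with an event and the group size. Section 8.2 defines days in trial and duration of exposure, but no AE analysis uses either.

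**The concern.** The length of observation is set by an event after randomisation. A completer who enters the extension stops contributing TEAEs soon after week 14, while one who does not is observed for about four more weeks. Entering the extension is partly the participant's choice and may depend on how the treatment period went, so the proportion entering could differ between active and placebo.

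If it does, the arm with fewer rollovers is observed longer on average and shows a higher crude incidence at the same underlying rate. If active participants roll over more often, the distortion runs against seeing an excess of harm; if less often, it creates an apparent excess. The final posterior probabilities inherit the same distortion because their model has no time term. Events late in the window are also seen only in the self-selected group that stayed for follow-up, yet they are expressed over all treated participants.

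**Working it through.** **Inputs from the SAP.** End-of-treatment visit day 99 ± 3; follow-up visit day 127 ± 3; last scheduled dose day 85 (Section 2.1). Exposure runs to four weeks past the last dose (Section 8.2). Planned size is 40 per arm per indication (Section 2.5), so 80 per arm with indications pooled.

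**Assumed, because the SAP gives no figure.** Incidence by day 99, rollover shares by arm, a constant hazard through day 127, and a first extension dose at about day 99. Appendix 4 lets extension baseline values serve for the week 14 CDAI, which suggests a short interval, but no day is stated.

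**1. The SAP's own figures.** Screening, treatment and follow-up give 6 + 14 + 4 = 24 weeks, matching the stated maximum participation. For the Beta(1,1) model, direct integration reproduces all eight rows of Table 14 within 0.001.

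**2. Size of the gap.** 127 − 99 = 28 days. With visit windows it runs from 124 − 102 = 22 to 130 − 96 = 34 days. The ratio is 127/99 = 1.28. A first extension dose later than day 99 shortens the gap.

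**3. Incidence by window.** With p99 the incidence by day 99:

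h = −ln(1 − p99)/99, p127 = 1 − exp(−127h) = 1 − (1 − p99)^(127/99).

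**4. Crude incidence by arm.** With rollover share r:

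m(r) = r·p99 + (1 − r)·p127, so the arm difference with equal hazards is m(rA) − m(rP) = −(rA − rP)(p127 − p99).

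Taking rA = 90% (active) and rP = 70% (placebo), with no true difference:

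| By day 99 | By day 127 | Active | Placebo | Difference (points) |
|---|---|---|---|---|
| 5% | 6.4% | 5.14% | 5.41% | −0.3 |
| 10% | 12.6% | 10.3% | 10.8% | −0.5 |
| 20% | 24.9% | 20.5% | 21.5% | −1.0 |
| 50% | 58.9% | 50.9% | 52.7% | −1.8 |

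Reversing the shares reverses the sign. Equal shares give exactly zero. The limiting case of 100% against 0% gives −1.4, −2.6, −4.9 and −8.9 points.

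**5. Effect on the posterior probability.** With 80 per arm, a 20% event by day 99 and no true difference, the chance that the posterior probability reaches 0.90 is:

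- 9.8% with rollover of 80% in both arms;
- 7.5% with 90% active and 70% placebo;
- 12.7% with 70% active and 90% placebo.

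The 0.90 is borrowed from the interim rules in Table 11 for illustration. Section 8.3 sets no cutoff at the final analysis.

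**6. Defined exposure against the two windows.** Day 85 + 28 = day 113. This matches neither end point, and 113 − 99 = 14 of the 28 extra days fall inside defined exposure.

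**The case against.** The strongest reply is that differential rollover is assumed, not shown. The extension may be offered to everyone. Section 4.2.1 refers to assignment to maintenance or re-induction in the extension, which suggests that response decides what a participant receives there and not whether they may enter. With equal rollover there is no bias between arms. This stands as a limit on size, but it does not make the window common.

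The effect is also small. One participant is 2.5 points at 40 per arm and 1.25 points at 80, against about 0.3 points for a 5% event with a 20-point gap. No formal decision depends on it: the TEAE tables are descriptive and the final posterior probabilities are only reported. Both points stand.

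A reader might infer that the SAP hides the imbalance. It does not. Section 5.2 counts completers by rollover or follow-up, and Section 5.1 presents those counts by treatment group. That shows whether the problem exists but corrects no AE result.

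A reader might also infer that the extra 28 days are all free of drug. They follow the end of dosing, but half of them lie within the exposure period defined in Section 8.2.

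Finally, ending TEAEs at the first extension dose is sensible in itself, since it keeps events under extension treatment out of this trial. The gap lies in having no analysis over a common window.

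**Conclusion.** The point holds in limited form. The unequal windows are explicit in Sections 2.1 and 8.3, and neither the crude incidences nor the final Beta-binomial analysis allows for them. Early withdrawals, who are only encouraged to complete follow-up, add to the inequality.

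The documents do not support saying that the AE comparison will be materially wrong, or in which direction. Bias between arms needs unequal rollover. For a 20-point gap it is about 0.3 to 1.8 points across event rates of 5% to 50%, assuming a constant hazard and an extension start at about day 99. A later start, or a lower event rate after dosing ends, would make it smaller.

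This is worth correcting because the data are already collected, the change is cheap, and a window chosen after rollover by arm is known would carry less weight. Separately, Sections 2.1 and 8.3 disagree on when AE collection ends for extension entrants. An event between extension randomisation and the first extension dose counts as a TEAE but falls outside the stated recording period of this trial's CRF.

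**What to change.** Keep the all-data TEAE tables and add to Sections 8.1 and 8.3, before unblinding:

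- **(a) Common cut-off.** Repeat the overview TEAE table and the final Beta-binomial analysis of the four AE types with events starting by nominal week 14 (day 99), or by the first extension dose if earlier, for every participant regardless of when dosing stopped.
- **(b) And/or rates.** Report exposure-adjusted incidence rates using each participant's time at risk within the TEAE window. The Section 8.2 duration of exposure is not a suitable denominator, since it nominally ends on day 113. Rates remove the window effect only as far as the hazard is roughly constant, so (a) is the cleaner choice if only one is added.
- **Later events.** Tabulate events starting after week 14 separately, with participants who entered follow-up as the denominator.
- **Recording end.** Reconcile extension randomisation in Section 2.1 with first extension dose in Section 8.3.

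A cut-off tied to the last dose, such as 14 days after it, should be avoided. A participant last dosed on day 29 would be cut at day 43, so the window would again depend on a post-randomisation event that can differ by arm.

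The cost is SAP wording and one extra set of AE tables, with no new data. The day 99 cut does not recover time lost when a participant leaves the trial before week 14.

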2.5. Sample Size and Power Considerations

A total trial sample size of approximately 240 participants is planned, with 120 participants (40 participants per dose arm) each for the 2 indications of UC and CD.

The sample size does not include participants that were randomized to the 1800 mg Q2W treatment group prior to Protocol Amendment 03 with Revision 01.

Assumptions:

The clinical remission and endoscopic response rates assumed in the sample size and related operating characteristics computations are as follows:

- Clinical remission rates in UC group: 8% for placebo; 30% for TEV-48574 groups, respectively
- Endoscopic response rates in CD group: 12% for placebo; 34% for TEV-48574 groups, respectively

Additional scenarios for remission (UC), response rates (CD) are assumed as outlined in [Table 2](#) to investigate the operating characteristics.

Table 2: Remission (UC), Response (CD) Rates Scenarios for Clinical Trial Simulations

Scenario	Indication	Placebo (%)	TEV-48574 450 mg Q2W (%)	TEV-48574 900 mg Q2W (%)
Null	UC	8	8	8
	CD	12	12	12

Table 2: Remission (UC), Response (CD) Rates Scenarios for Clinical Trial Simulations (Continued)

Scenario	Indication	Placebo (%)	TEV-48574 450 mg Q2W (%)	TEV-48574 900 mg Q2W (%)
Intermediate Efficacy	UC	8	20	20
	CD	12	25	25
Efficacy	UC	8	30	30
	CD	12	34	34
Efficacy-high dose only	UC	8	8	30
	CD	12	12	34

CD=Crohn's disease; Q2W=every 2 weeks; UC=ulcerative colitis.

Operating Characteristics:

Simulation-based operating characteristics for the analysis of the primary efficacy variable using a Bayesian Beta Binomial model are presented in [Table 3](#). This model uses a posterior probability cutoff of ≥ 0.90 to declare success at the final analysis.

Table 3: Operating Characteristics of Final Analysis

	UC			CD		
	TEV-48574 450 mg Q2W	TEV-48574 900 mg Q2W	At least 1 dose	TEV-48574 450 mg Q2W	TEV-48574 900 mg Q2W	At least 1 dose
Null	7.9%	7.9%	13.5%	9.6%	9.6%	16.1%
Intermediate efficacy	61.1%	61.1%	77.3%	59.3%	59.3%	75.9%
Efficacy	91.0%	91.0%	97.6%	87.1%	87.3%	95.5%
Efficacy-high dose only	7.9%	91.1%	91.1%	9.6%	87.2%	87.3%

CD=Crohn's disease; Q2W=every 2 weeks; UC=ulcerative colitis.

Beta-Binomial model with non-informative prior Beta(1,1); decision rule for declaring difference from placebo is based on having a posterior probability of ≥ 0.90 .

Note: Operating characteristics based on 500,000 simulations.

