4.3. Handling Withdrawals and Missing Data

Unless specified otherwise in this section, for all variables, only observed data will be used in the statistical analyses; i.e., there is no plan to estimate missing data.

All binary response and remission variables will be imputed as non-response if any of the following cases occur:

- Participants discontinuing treatment and/or trial during the 14-week treatment period regardless of the reason
- Participants who used rescue medications for UC or CD prior to their week 14 evaluation of remission/response (see [Section 4.5](#) for classification rules)
- Participants undergoing major UC or CD related surgery (see [Section 4.6](#) for classification rules)

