13.1. Interim Safety Analyses

Periodic analysis of safety data will be done during the trial.

For each of the 4 types of AEs listed in Table 11, a Bayesian analysis using the Beta-binomial model with a non-informative *Beta* (1, 1) prior will be conducted. The posterior probability of each type of AE will be compared for each dose and the 2 dose levels combined versus placebo. If the posterior probability that the AE rate in the active group is greater than the AE rate in the placebo group reaches a posterior probability cutoff defined below, the stopping rule will be triggered. The analyses and evaluation will be conducted for UC and CD separately and across the entire trial population.

Table 11: Safety Stopping Criteria

AE Type	Posterior Probability Cutoff
Serious adverse events (aggregated)	90%
Grade 3/4 adverse events (aggregated)	90%
Opportunistic and severe and/or serious infections	85%
Anaphylaxis	85%

[figure not shown]
Details on the Beta-binomial model are provided in [Appendix 1](#).

The “basic process” for applying the safety stopping rules is presented in [Figure 1](#).

The safety interim analysis comprises of the following steps:

- Step 1: CD and UC separately, for each type of AE
 - Apply the “basic process” for each indication separately
- Step 2: Combine indications, for each type of AE (not applicable if one indication is stopped)
 - Apply the “basic process” to the combined data from both indications, excluding the dose(s) that were stopped in each indication (if applicable)
- Step 3: Detailed review
 - Review in detail any safety signal that meets the safety stopping rule, taking into account the totality of safety data
- Step 4: IDMC recommendation
 - Make a recommendation if the safety signal warrants stopping the dose/indication/trial

Steps 1 and 2 will be performed periodically by the unblinded analysis group. The Bayesian stopping rules analysis will be performed by the unblinded statistician on a monthly basis, starting after 24 participants are randomized to the trial. Steps 3 and 4 will be performed by the IDMC in case any of the stopping rules is triggered.

Figure 1: Safety Stopping Rules – Basic Process

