Let $x_d^{i,k}$ be the number of participants in the indication and active dose group experiencing an AE of the selected type

$x_0^{i,k}$ be the number of participants in the indication in the placebo group experiencing an AE of the selected type

Using a non-informative *Beta* (1,1) prior, the posterior probabilities in the active dose group and placebo group are given by

$$\begin{aligned}\pi_d^{i,k} &\sim \text{Beta}\left(1 + x_d^{i,k}, 1 + (n_d^i - x_d^{i,k})\right) \\ \pi_0^{i,k} &\sim \text{Beta}\left(1 + x_0^{i,k}, 1 + (n_0^i - x_0^{i,k})\right)\end{aligned}$$

The safety stopping rule is given by

$$\text{Prob}(\pi_d^{i,k} > \pi_0^{i,k}) > C^k$$

where C^k is the posterior probability cutoff for the AE type (see Section 13.1, Table 11).

The posterior probability will be estimated as described above for the efficacy analysis.

Numerical examples of the pre-defined safety stopping rules are presented in [Appendix 2](#).

APPENDIX 2. SAFETY STOPPING RULES**Table 12: Safety Stopping Rules – Example 1: Single TEV-48574 dose vs placebo, 18 participants, stopping criterion: 90%**

		Placebo (Number of Participants With Event / Number of Participants)		
		0/9	1/9	2/9
TEV-48574 (Number of Participants With Event / Number of Participants)	0/9	0.500	0.237	0.106
	1/9	0.763	0.500	0.290
	2/9	0.895	0.709	0.500
	3/9	0.956	0.848	0.686
	4/9	0.984	0.929	0.824
	5/9	0.995	0.971	0.915
	6/9	0.998	0.990	0.965
	7/9	1.000	0.997	0.988
	8/9	1.000	0.999	0.997
	9/9	1.000	1.000	1.000

For each combination, the posterior probability that the event rate in the active group is higher than the event rate in the placebo group is presented

Table 13: Safety Stopping Rules – Example 2: Pooled TEV-48574 vs placebo, 36 participants, stopping criterion: 90%

		Placebo (Number of Participants With Event / Number of Participants)		
		0/9	1/9	2/9
TEV-48574 (Number of Participants With Event / Number of Participants)	0/27	0.263	0.064	0.014
	1/27	0.463	0.164	0.048
	2/27	0.611	0.279	0.103
	3/27	0.723	0.396	0.173
	4/27	0.804	0.507	0.257
	5/27	0.863	0.608	0.348
	6/27	0.906	0.694	0.440
	7/27	0.936	0.767	0.531
	8/27	0.958	0.827	0.615
	9/27	0.972	0.873	0.691
	10/27	0.982	0.909	0.759
	11/27	0.989	0.937	0.815
	12/27	0.993	0.957	0.862
	13/27	0.996	0.972	0.900
	14/27	0.998	0.982	0.930
	15/27	0.999	0.989	0.953

For each combination, the posterior probability that the event rate in the active group is higher than the event rate in the placebo group is presented

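### TEAEs with missing seriousness are reported as non-serious, and the SAP does not say how they enter the Beta-binomial serious AE counts

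*SAP*

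**What the plan says.** SAP Section 8.3, in the paragraph on TEAE incidence tables, fixes the handling: "TEAEs that are missing information on seriousness will be excluded from the summary of serious TEAEs but included in the summary of non-serious TEAEs". The overview table in the same section counts "Participants with at least 1 serious TEAE", so the unit affected is the participant.

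Section 4.3 sets the general position on missing data. Outside the exceptions it lists, analyses use what was observed and "there is no plan to estimate missing data". AE seriousness is not among those exceptions.

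Serious AEs appear again in two inferential places. Section 13.1 (Table 11) makes them a stopping-rule event type with a 90% posterior probability cutoff, run monthly once 24 participants are randomized. Section 8.3 then plans, on the final data, "A Beta-binomial analysis of the 4 types of AEs used to define the stopping criteria in the interim safety analyses". Neither place, nor Appendix 1, says what happens to an event whose seriousness is unknown.

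All AEs are listed (end of Section 8.3), so such an event stays visible at participant level.

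**The concern.** The rule resolves an unknown in the direction that makes the safety table look better. The SAP does the opposite for a missing efficacy outcome: Section 4.3.1 counts a missing week 14 endoscopy as non-response. No reason is given for the favourable choice on seriousness. There is also no separate category for unknown seriousness and no sensitivity count.

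Two things are at stake. The reported serious TEAE rate in an arm could be too low. And if an analyst carries the only rule the SAP states into the Beta-binomial counts, a single open field could decide whether the 90% cutoff is reached, because serious AE counts are small.

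**Working it through.** **Direction within one arm.** Let s be the participants with at least one TEAE known to be serious. Let m be those with none known to be serious but at least one of unknown seriousness, and n the arm size.

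- Rate under the SAP rule: s/n
- Rate with unknown taken as serious: (s + m)/n

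The true rate lies between the two, so the SAP rule reports the lower bound. It changes nothing if the participant already has another serious TEAE, or if the event was truly non-serious. With n = 40 and m = 1 the gap is 1/40 = 2.5 percentage points.

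**Inputs for the Beta-binomial check.**
- Model: Beta(1,1) prior in each arm (Section 13.1, Appendix 1).
- Cutoff for serious AEs: 90% (Table 11).
- Arm size: 9 per arm as in Table 12 of Appendix 2, and 40 per arm as planned ("120 participants (40 participants per dose arm) each for the 2 indications of UC and CD", Section 2.5).
- Number of participants with missing seriousness: not given. One is assumed, with no other serious TEAE.

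**Formula.** With x events among n in each arm (d = active, 0 = placebo), the posteriors are Beta(1 + x, 1 + n − x). Then P(π_d > π_0) is the integral over t of the active density times the placebo distribution function. When placebo has no events this reduces to

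P = 1 − B(1 + x_d, n_d − x_d + n_0 + 2) / B(1 + x_d, n_d − x_d + 1).

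**Reproducing the plan's own figures (Table 12, 9 per arm).**
- 2/9 vs 0/9: 1 − (8·9·10)/(18·19·20) = 1 − 720/6840 = 0.8947; the SAP prints 0.895.
- 3/9 vs 0/9: 1 − (7·8·9·10)/(17·18·19·20) = 1 − 5040/116280 = 0.9567; the SAP prints 0.956.
- 3/9 vs 1/9, by integration: 0.8483; the SAP prints 0.848.

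The cells checked in Tables 12, 13 and 14 agree within 0.001.

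**One participant at 40 per arm.**
- 2/40 vs 0/40: 1 − (39·40·41)/(80·81·82) = 1 − 63960/531360 = 0.8796.
- 3/40 vs 0/40: 1 − (38·39·40·41)/(79·80·81·82) = 1 − 2430480/41977440 = 0.9421.
- 3/40 vs 1/40, by integration: 0.8204.

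| Arm with the unknown event | Unknown as non-serious | Unknown as serious |
|---|---|---|
| Active, 9 per arm | 2 vs 0: 0.895 | 3 vs 0: 0.957 |
| Active, 40 per arm | 2 vs 0: 0.880 | 3 vs 0: 0.942 |
| Active, 40 per arm | 4 vs 1: 0.899 | 5 vs 1: 0.946 |
| Placebo, 9 per arm | 3 vs 0: 0.957 | 3 vs 1: 0.848 |
| Placebo, 40 per arm | 3 vs 0: 0.942 | 3 vs 1: 0.820 |

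Every row crosses 0.90. An unknown event on active makes the SAP rule the less sensitive choice. An unknown event on placebo makes it the more sensitive one.

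**One unknown event in each arm (40 per arm, 2 known on active, 0 on placebo).** Both as non-serious gives 2 vs 0, 0.880. Both as serious gives 3 vs 1, 0.820. Serious in the active arm only gives 3 vs 0, 0.942. Neither uniform rule yields the highest probability here, which is why the worst case has to be run separately.

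**The case against.** The strongest reply has four parts.

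1. **Scope.** The sentence governs descriptive tables. The Beta-binomial analysis is a separate paragraph, and neither Section 13.1 nor Appendix 1 refers to the rule. This stands: the crossing of 0.90 is conditional on an assumption about what feeds those counts. What remains is that the SAP leaves the handling open.

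2. **Consequences.** A triggered rule leads to detailed IDMC review in the light of all the safety data and then a recommendation, not to an automatic stop. The run is monthly, so a field completed later enters the next one. Grade 3/4 events and severe or serious opportunistic infections have their own criteria. At the final analysis the probability is only reported. All of this stands and limits the stakes.

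3. **Visibility.** The events remain in the all-TEAE and by-grade summaries and in the AE listing. This also stands, though the headline serious TEAE rate is still the lower bound.

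4. **Direction.** A reader might infer that the rule systematically hides harm in the comparison with placebo, and that reversing it could never understate harm. The documents do not support either inference. The one-sided direction holds for a rate within an arm. For the contrast, an unknown event on placebo counted as serious takes 3/40 vs 0/40 from 0.942 to 0.820 and removes a trigger that the SAP's rule would leave in place.

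**Conclusion.** The point holds as a minor one. For the descriptive serious TEAE summaries, the stated rule is anti-conservative: the rate in an arm can only fall or stay the same, by 2.5 percentage points for each affected participant at 40 per arm.

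For the Beta-binomial serious AE analyses the defect is silence, not a demonstrated bias. If the rule does carry over, one participant can decide whether 0.90 is reached, in either direction according to arm. That rests on one affected participant with no other serious TEAE, on counts near the cutoff, and on 40 (or 9) participants per arm; actual safety-set sizes may differ. How many TEAEs will lack seriousness is not stated, and it may be none at database lock. A reader might also infer that interim data will hold many open seriousness fields; the SAP gives no figure for that.

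**What to change.** Section 8.3: count TEAEs with missing seriousness as serious in the serious TEAE summaries, and flag them in the AE listing.

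Sections 8.3 and 13.1, with Appendix 1: state how such events enter the interim and final Beta-binomial serious AE counts. Report the posterior probability with missing as serious and with missing as non-serious, and add missing as serious in the active arms only as the worst case. The last is needed because a uniform reversal can lower the probability when the unknown event is on placebo.

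The cost is a few sentences and one extra sensitivity run. The serious AE rate may be slightly overstated until queries are resolved. If no seriousness field is missing, all versions coincide.
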